3. To assess the impact of co-administration of *Na*-GST-1 and *Na*-APR-1 (M74) on the functional capacity of vaccine-induced antibodies to neutralize the *in vitro* activity of the native enzymes (*Na*-GST-1 and wild type *Na*-APR-1).
4. To assess the impact of co-administration of *Na*-GST-1 and *Na*-APR-1 (M74) on the affinity of the antibody interactions with both recombinant antigens.
5. To assess the impact of co-administration of *Na*-GST-1 and *Na*-APR-1 (M74) on the production of memory B cells specific for each antigen.

Description of Study Design:

Double blind, randomized, controlled, dose-escalation Phase 1 clinical trial in hookworm exposed adults living in the area of Americaninhas, Minas Gerais, Brazil. Subjects will receive three

doses of the assigned vaccine delivered intramuscularly on approximately Days 0, 56, and 112.

Safety will be measured from the time of each study vaccination (Day 0) through 14 days after each study vaccination by the occurrence of solicited injection site and systemic reactogenicity events.

Unsolicited non-serious adverse events (AEs) will be collected from the time of the first study vaccination through approximately 1 month after each study vaccination. New-onset chronic medical conditions and Serious Adverse Events (SAEs) will be collected from the time of the first study vaccination through approximately 9 months after the third study vaccination (final visit). Clinical laboratory evaluations for safety will be performed on venous blood collected approximately 14 days after each vaccination.

Immunogenicity testing will include IgG antibody responses to each vaccine antigen, by an indirect enzyme-linked immunosorbent assay (ELISA) and also by ImmunoCAP, on serum obtained prior to each study vaccination and at time points after each vaccination (see Appendix A); antibody affinity by Surface Plasmon Resonance; functional activity of vaccine-induced antibodies via *in vitro* enzyme neutralization assays; and, antigen-specific memory B cell responses.

Recruitment and enrollment into the study will occur on an ongoing basis, with each group being recruited and vaccinated in sequence.

60 subjects will be enrolled into 6 groups of 10:

The first 20 subjects will be entered into Groups 1 and 2 through open sequential enrollment.

- Group 1 double-blind IP allocation (n=10):

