3.2.3 Tertiary Outcome Measures

Immunogenicity

The following parameters will be evaluated for each dose and formulation of *Na*-APR-1 (M74) alone or co-administered with *Na*-GST-1:

1. The IgG antibody response, by an indirect enzyme-linked immunosorbent assay (ELISA) at approximately 7, 14, and 28 days after each vaccination, and approximately 3, 6, and 9 months after the third dose.

2. The IgG antibody response, by ImmunoCAP at approximately 7, 14, and 28 days after each vaccination, and approximately 3, 6, and 9 months after the third dose.
3. The IgG subclass distribution (IgG1, IgG3, and IgG4) by plate based ImmunoCAP on approximately Day 126.
4. The IgG subclass distribution by plate based ImmunoCAP each day of vaccination, approximately 28 days later, and approximately 3 and 6 months after the final vaccination.
5. The functional capacity of vaccine-induced antibodies to neutralize the *in vitro* activity of the native enzymes.
6. The affinity of the antibody interactions with both recombinant antigens at approximately 7, 14, and 28 days after each vaccination, and 3, 6, and 9 months after the third dose.
7. The production of memory B cells specific for each antigen on days of vaccination, approximately 28 days following each vaccination, and 6 and 9 months after the third dose.

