4 STUDY DESIGN

The study will be conducted as a randomized, placebo-controlled, double-blind Phase 1 dose-escalating clinical trial in healthy adult volunteers living in the hookworm-endemic area of Americaninhas, Brazil.

Prior to beginning study-related activities, the consent and cooperation of local municipal government leaders and representative community members will be sought, after which volunteers will be invited to participate in the study. After providing written informed consent and passing the informed consent comprehension questionnaire, volunteers will undergo eligibility screening, including a complete medical history, physical examination, hematology testing, serum glucose testing, liver and renal function testing, HIV antibody testing, Hepatitis B and C serology, and urinalysis; urine pregnancy testing will be performed on all female volunteers. In addition, all volunteers will be tested for serum IgE antibodies to *Na*-APR-1 (M74) and *Na*-GST-1, and a fecal examination will be performed for ova and parasites. All clinically significant abnormalities will be reviewed with volunteers and referral for follow-up care will be provided. After screening, those volunteers determined to be eligible, based on the inclusion and exclusion criteria, will be invited to participate in the study.

Sixty volunteers will be progressively enrolled into 1 of 6 Groups over a projected 3-month enrollment period, with each subject followed for 13 months post-enrollment (to Study Day 380). Group enrollment will be done in an open sequential fashion, whereas within each Group, investigational product (IP) assignment and vaccination will be done in a randomized double-blind fashion.

The first 20 subjects will be entered into Groups 1 and 2

- Group 1 double-blind IP assignment (n=10):
 - 5 subjects will receive 10µg *Na*-APR-1 (M74) delivered by IM injection in the deltoid muscle, with sterile saline administered to the alternate arm.
 - 5 subjects will receive 10µg *Na*-APR-1 (M74) delivered by IM injection in the deltoid muscle, with 100µg *Na*-GST-1 administered to the alternate arm.
- Group 2 double-blind IP assignment (n=10):
 - 5 subjects will receive 10µg *Na*-APR-1 (M74) plus 5µg GLA-AF delivered by IM injection in the deltoid muscle, with sterile saline administered to the alternate arm.

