5.3 Treatment Assignment Procedures

5.3.1 Randomization Procedures

Eligible volunteers will be asked to come to the clinic on their scheduled day of enrollment into the study (Day 0). If required, transportation to the clinic will be provided free-of-charge. One or 2 additional eligible volunteers above the number to be enrolled into a given Group may be scheduled as Day 0 visit alternates, if possible. After undergoing a clinical interview and physical examination to ensure that they remain eligible for participation in the study, that they have had blood collected for safety clinical laboratory and baseline immunogenicity assessments, and that females have had a urine pregnancy test performed that is documented to be negative, volunteers will be randomized and enrolled in the order that they present for vaccination.

Within each group, randomization will be done through use of a randomization code, furnished to the study vaccine manager by the data management center. Access to the randomization list will be exclusively limited to the study vaccine manager and assistant. Between vaccination days, the randomization list will be stored in a locked cabinet. The study vaccine manager and assistant will be unblinded, but will not be involved in further evaluation of study subjects or assessment of adverse events. Volunteers will not be considered enrolled in the study until they have received their first dose of vaccine. In the event that a volunteer is randomized but not enrolled on the day of first vaccination, they will be replaced with an eligible alternate. Enrolled subjects that leave the study for any reason following first vaccination will not be replaced. Any alternates not vaccinated will be invited to participate as members of the next Group. Any Group 6 alternates not vaccinated, and therefore not enrolled in the study, will be offered vaccination with a non-study, licensed vaccine such as the tetanus toxoid or influenza vaccine.

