11.4 Final Analysis Plan

The purpose of this trial is to estimate AE rates and patterns of immune response as well as to compare these rates and patterns between the investigational vaccines, when they are administered separately or when they are co-administered.

This section briefly describes the statistical methods to be used; a detailed analytical plan will fully describe the methods. The analytical plan will discuss the planned approaches to missing data. Deviations from the original analytical plan will be thoroughly documented and reported to the Sponsor.

Descriptive and hypothesis-testing approaches will be used to meet the protocol objectives as stated in **Section 3**. Estimates will be presented with their 95% confidence intervals. Formal statistical tests, as outlined below, will be used to compare doses. Statistical tests will use a two-sided significance level of 5%.

Note: For the analyses described below, historical safety data from a Phase 1 clinical trial conducted at the same study site and in the same subject population (study SVI-10-01, see **Section 2.1.6** above for a description of this trial) will be used to obtain a comparison of *Na*-GST-1/Alhydrogel. As well, stored serum and cell specimens from those study participants will be used in the immunological assays to obtain data on subjects administered *Na*-GST-1/Alhydrogel without co-administered *Na*-APR-1 (M74). These specimens from SVI-10-01 will be assayed at the same time as those newly collected from the study described in this protocol.

Primary Objective: To evaluate the safety and reactogenicity of three different dose concentrations of Na-APR-1 (M74) adjuvanted with Alhydrogel® or Alhydrogel® plus GLA-AF and administered either with or without Na-GST-1, in healthy Brazilian adults.

AEs will be coded according to Medical Dictionary of Regulatory Activities (MedDRA™) preferred terms. The frequency, severity, and relationship of AEs per each vaccine formulation and dose cohort of Na-APR-1 (M74) and co-administration status with Na-GST-1 will be presented in tabular form using the MedDRA™ coded term and organized by MedDRA™ System, Organ, and Class (SOC) designations.

- The frequency of immediate, systemic, and local injection site AEs will be summarized by SOC and preferred term.

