- d. For antigen-specific IgG subclass (IgG1-IgG4) levels, a three-way ANOVA will be conducted, with Na-APR-1 (M74) and GLA-AF doses, and Na-GST-1 co-administration status, as factors.
 - e. A longitudinal model will be built to describe each of the antibody isotype levels over time for each of IgG1-IgG4. Using a longitudinal panel model, differences in antibody isotype levels by dose and formulation of Na-APR-1 (M74) and Na-GST-1 co-administration status will be explored. This will be accomplished using Proc Mixed in SAS 9.3 so the analysis will take account of the correlation between measurements on the same participant.

Tertiary Objective 3: To assess the impact of co-administration of Na-GST-1 and Na-APR-1 (M74) on the functional capacity of vaccine-induced antibodies to neutralize the *in vitro* activity of the native enzymes (Na-GST-1 and wild type Na-APR-1).

Tertiary Outcome Measure 5: The functional capacity of vaccine-induced antibodies to neutralize the *in vitro* activity of the native enzymes.

Analysis Plan:

- a. Percent inhibition of native enzyme activity will be displayed graphically for the various study groups at each time point.
- b. Three-way ANOVAs with Na-APR-1 (M74), Na-GST-1, and GLA-AF as factors and percent inhibition as the outcome will be estimated.
- c. A longitudinal model will be built to describe percent inhibition of native enzyme activity over time. Using a longitudinal panel model, differences in percent inhibition by dose and formulation of Na-APR-1 (M74) and co-administration with Na-GST-1 will be explored. This will be accomplished using Proc Mixed in SAS 9.3, so the analysis will take account of the correlation between measurements on the same participant.

Tertiary Objective 4: To assess the impact of co-administration of Na-GST-1 and Na-APR-1 (M74) on the affinity of the antibody interactions with both recombinant antigens.

Tertiary Outcome Measure 6: The affinity of the antibody interactions with both recombinant antigens at approximately 7, 14, and 28 days after each vaccination, and 3, 6, and 9 months after the third dose.

Analysis Plan:

- a. Antibody affinity will be displayed graphically for the various study groups at each time point.
- b. Three-way ANOVAs with Na-APR-1 (M74), Na-GST-1, and GLA-AF as factors and overall affinity as the outcome will be estimated.

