- c. A longitudinal model will be built to describe increasing antibody affinity (affinity maturation) over time. Using a longitudinal panel model, differences in affinity maturation by dose and formulation of *Na*-APR-1 (M74) and co-administration with *Na*-GST-1 will be explored. This will be accomplished using Proc Mixed in SAS 9.3, so the analysis will take account of the correlation between measurements on the same participant.

Tertiary Objective 5: To assess the impact of co-administration of *Na*-GST-1 and *Na*-APR-1 (M74) on the production of memory B cells specific for each antigen.

Tertiary Outcome Measure 7: The production of memory B cells specific for each antigen on days of vaccination, approximately 28 days following each vaccination, and 6 and 9 months after the third dose.

Analysis Plan:

- a. The amount of *Na*-GST-1 and *Na*-APR-1 (M74) specific memory B cells will be expressed as a percentage of total lymphocytes present in the blood.
- b. The percentage of specific memory B cells will be displayed graphically by study group at each time point.
- c. Two separate longitudinal panel analyses will test the null hypothesis that average percentages for each of memory B cells are the same in *Na*-APR-1 (M74) groups with and without co-administration of *Na*-GST-1 over time. This will be accomplished using Proc Mixed in SAS 9.3 so the analysis will take account of the correlation between measurements on the same participant.
- d. Mann-Whitney tests will assess the null hypothesis that cytokine levels are the same in the groups at the primary time point of Day 126, two weeks after final vaccination.

Exploratory Objective: To assess the cellular immune responses to the *Na*-GST-1 and *Na*-APR-1 (M74) antigens following immunization.

The following assays will be performed to assess the cellular immune responses to vaccination with *Na*-APR-1 (M74) +/- *Na*-GST-1:

- a. Lymphocyte proliferative responses to *in vitro* stimulation with *Na*-GST-1 or *Na*-APR-1 (M74).
- b. Cytokine and chemokine production *in vitro* in response to stimulation with *Na*-GST-1 or *Na*-APR-1 (M74).
- c. Changes in *in vivo* PBMC subpopulations as determined by flow cytometry.
- d. A longitudinal panel analysis will test the null hypothesis that cytokine and chemokine levels are the same when *Na*-APR-1 (M74) is administered with and without or *Na*-GST-1 and examine for trends over time.

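### The memory B cell and cytokine longitudinal comparisons name no Na-APR-1 dose or GLA-AF factor, although product is randomised within six dose/adjuvant Groups: a low-stakes point with a nearly free improvement

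*Protocol*

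**What the plan says.** The Protocol Summary states that "60 subjects will be enrolled into 6 groups of 10". The Groups are filled in sequence and differ by Na-APR-1 dose (10, 30 or 100 µg) and by GLA-AF (0 or 5 µg). Section 4 adds that "within each Group, investigational product (IP) assignment and vaccination will be done in a randomized double-blind fashion", with five subjects on saline and five on Na-GST-1 in each Group. Section 5.3.1 agrees: "Within each group, randomization will be done through use of a randomization code".

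Section 3.2.3 introduces the tertiary outcomes, memory B cells among them, with "The following parameters will be evaluated for each dose and formulation of" Na-APR-1, alone or co-administered. Section 3.2.4 says the same of the cellular responses.

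In section 11.4, the longitudinal models for Tertiary Objectives 1 to 4 name dose and formulation together with co-administration. The neutralisation model, for example, explores "differences in percent inhibition by dose and formulation of" Na-APR-1 and co-administration. Three-way ANOVAs on the three product factors are listed for these objectives too.

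Tertiary Objective 5 item c is worded differently: "Two separate longitudinal panel analyses will test the null hypothesis that average percentages for each of memory B cells are the same in" Na-APR-1 groups with and without Na-GST-1 over time, using Proc Mixed to handle repeated measurements on a participant. Exploratory item d reads: "A longitudinal panel analysis will test the null hypothesis that cytokine and chemokine levels are the same when" Na-APR-1 is given with or without Na-GST-1, with trends over time also examined. No three-way ANOVA is listed for either endpoint.

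**The concern.** The comparison that randomisation supports is Na-GST-1 versus saline within a Group. The Groups span a ten-fold range of antigen dose and the presence or absence of an immunostimulant, so their mean responses may well differ. Because allocation is balanced in every Group, those differences cancel from the overall co-administration estimate. They do not cancel from the residual variance unless the model contains Group, or dose and GLA-AF. A model with co-administration alone would then report a standard error larger than the real variability of its own estimate.

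The direction matters. Hypothesis 5 in section 11.1 is that co-administration will not decrease memory B cell induction, so lost sensitivity makes a real decrease easier to miss.

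**Working it through.** **Inputs from the protocol.** Six Groups, 5:5 in each, hence 30 versus 30 overall; two-sided 5% level (section 11.4).

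**The protocol's own figures.** The only sample-size figures are the event-detection probabilities in section 11.2. They reproduce: for N=30 and a 5% rate, 1 − 0.95^30 = 78.54%. Nothing comparable exists for the memory B cell or cytokine comparisons.

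**Assumptions.** No effect size, variance or between-Group spread is given. I work on each subject's time-averaged response, take its within-Group SD as 1, and let the six Group means have SD *s*. The true difference is set at 0.737 within-Group SD, which gives 80% power with Group in the model. Data are complete.

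**Step 1, real precision.** The estimate averages six within-Group differences, so its SD is √(2/30) = 0.258 whatever the value of *s*.

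**Step 2, reported precision without Group.** The residual sum of squares has expectation 58 + 60*s*² on 58 degrees of freedom. The standard error is therefore inflated by √[(58 + 60*s*²)/58], which is close to √(1 + *s*²):

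- *s* = 0.5: √(73/58) = 1.12
- *s* = 0.75: √(91.75/58) = 1.26
- *s* = 1.0: √(118/58) = 1.43

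**Step 3, size and power** (simulation, co-administration-only model on 58 df against co-administration plus Group on 53 df):

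| *s* | Size, no Group | Power, no Group | Size, with Group | Power, with Group |
|---|---|---|---|---|
| 0 | 5.0% | 80% | 5.0% | 80% |
| 0.5 | just under 3% | 73% | 5.0% | 80% |
| 0.75 | 1.4% | 63% | 5.0% | 80% |
| 1.0 | about 0.6% | 50% | 5.0% | 80% |

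Main effects for dose and GLA-AF in place of six Groups give the same result when the Group differences are additive. A small random-intercept run (150 trials per setting, seven visits) showed the same pattern at *s* = 1.0: power 54% without the factors and 79% with them.

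**Step 4, the test over time.** If the test is co-administration by visit in a random-intercept model, Group differences that are constant over visits drop out within subject. Group differences that develop after vaccination do not, and a dose or adjuvant effect on a vaccine response is of that kind. A Group main effect alone would not remove them; Group-by-visit is needed.

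**Step 5, which antigen.** The saline arm receives no Na-GST-1. For Na-GST-1-specific cells, with versus without therefore measures the response to the antigen itself. Section 11.4 obtains the Na-GST-1-alone comparison from stored serum and cell specimens of SVI-10-01. Within this trial, the interference question is confined to Na-APR-1-specific responses.

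**The case against.** The strongest reply is that items c and d state a null hypothesis, not a list of model terms. They do not exclude dose and GLA-AF, and section 11.4 calls itself brief and defers detail to an analytical plan that is not at hand. That stands, so a reader should not infer that the protocol commits to pooling across Groups. What remains is that section 11.4 names these factors in every longitudinal model for Objectives 1 to 4 and drops them here, so an analytical plan written faithfully to the text could carry the omission forward.

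Second, the size of the loss is assumed, and it is nil if the Groups do not differ. Section 2.2.2 reports that GLA-AF did not significantly raise IgG to Na-GST-1. That also stands, although here GLA-AF is mixed with a different antigen, and section 2.1.11 says that adding MPL, the related adjuvant, often much improves the antibody response.

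Third, a reader might infer that outcome measure 7 goes undelivered. It does not: item b plots memory B cells by study group at each time point, and section 11.1 describes the study as primarily descriptive. What is missing is any stated model-based estimate by dose and formulation.

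Fourth, it is tempting to call item c the only inference on hypothesis 5. That overreaches, because the hypothesis covers both antigens and the Na-GST-1 half rests on the SVI-10-01 specimens.

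**Conclusion.** The point holds as a low-stakes improvement. The wording for these two endpoints departs from the rest of section 11.4 and from the randomisation. Taken literally, it gives an unbiased but needlessly imprecise co-administration comparison. Under assumed Group-mean SDs of 0.5, 0.75 and 1.0 within-Group SD, intervals are about 12%, 26% and 43% too wide, and power drops from about 80% to about 73%, 63% and 50%. With no Group differences there is no loss. These figures assume complete 5:5 data and a test on the time average.

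One might read the shrunken test size as a failure of validity. The documents do not support that: the error is conservative, with no bias and no excess of false positives. Nor does it undermine a powered conclusion, since the endpoints are tertiary and exploratory and section 11.2 claims no power for differences between groups.

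**What to change.** In Tertiary Objective 5 item c and Exploratory item d, state that the longitudinal model includes Group (Na-APR-1 dose by GLA-AF, six levels) and Group-by-visit, alongside co-administration, visit and co-administration-by-visit. Item d names no procedure, and section 11.3.2 mentions generalized estimating equations for cytokines over time; the same terms apply whichever is used. Report the co-administration estimate both within and across Groups, treating the 5-versus-5 within-Group estimates as descriptive. Say that the interference reading applies to Na-APR-1-specific responses, and refer to the SVI-10-01 comparison for Na-GST-1.

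The cost is a sentence or two and no new data. Group takes 5 of 58 between-subject degrees of freedom. With the eight memory B cell visits in outcome measure 7, Group-by-visit takes 5 × 7 = 35 of the 60 × 7 − 7 − 7 = 406 within-subject degrees of freedom available with complete data.

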12 SOURCE DOCUMENTS AND ACCESS TO SOURCE DATA/DOCUMENTS

Complete source documentation (clinical evaluations and test results) will be collected for every study subject for the duration of the study, with supplementary documents (laboratory test reports, supplementary hospital or medical records, etc.) forming part of the source documentation. Case Report Forms (CRFs) will be used to record study-specific data for enrolled subjects, and study-specific data may be entered directly onto CRFs: in these cases, the documents will be both source and CRF. The Principal Investigator will be responsible for the accuracy and completeness of the data reported in the CRFs and the source documents. Data reported in the CRFs that is derived from source documents should be consistent with source documents and the discrepancies should be explained.

